Title of the document	Clinical Research Protocol
Title of the study	Phase II, multi-center, randomized, double-masked clinical study to evaluate the safety and efficacy of the PRO-157 ophthalmic solution in three different posologies versus Moxifloxacin and versus Gatifloxacin in patients with bacterial conjunctivitis.
Study drug	Pazufloxacin
Indication	Antibiotic for the treatment of bacterial conjunctivitis
Development phase	Phase II
Protocol Code	SOPH157 - 0114 / II
Sponsor	Sophia Laboratories, S.A. of C.V.
Version 4	April 2016

1.- SUMMARY STUDY

Sponsor's name: Laboratorios Sophia, S.A. of C.V.	
Finished Product Name: NA	
Active Ingredient Name: Pazufloxacin	
Title of the study: Phase II clinical study, multicenter, randomized, double masked to evaluate the safety and efficacy of the ophthalmic solution PRO-157 in three different posologies versus Moxifloxacin and versus Gatifloxacin in patients with bacterial conjunctivitis.	
Study centers: To be defined	
Study period: 7 days	Phase of development of the study: Phase II
Objectives:	
General purpose:	
To evaluate the safety and efficacy of the ophthalmic solution PRO-157 in three different posologies versus Moxifloxacin and versus Gatifloxacin in patients with bacterial conjunctivitis.	
Specific objectives:	
To determine the safety of the PRO-157 solution in three different posologies versus Moxifloxacin and versus Gatifloxacin in patients with bacterial conjunctivitis by the incidence of adverse events.	
To evaluate the efficacy of the ophthalmic solution PRO-157 in three different posologies versus Moxifloxacin versus Gatifloxacin in patients with bacterial conjunctivitis through the evaluation of ocular signs and symptoms such as: burning, lacrimation, foreign body sensation, pruritus, photophobia, hyperemia conjunctival, chemosis, secretion, membranes and / or pseudomembranes, scales and palpebral edema, epitheliopathy.	
Work hypothesis	
The ophthalmic solution PRO-157 is so safe and effective in any of its different posologies when demonstrating non-inferiority when compared against Moxifloxacin and Gatifloxacin in the treatment of bacterial conjunctivitis.	
Ho: The ophthalmic solution PRO-157 is not as safe and effective in any of its different dosages when demonstrating non-inferiority when compared against Moxifloxacin and Gatifloxacin in the treatment of conjunctivitis	
Ha: The ophthalmic solution PRO-157 is so safe and effective in some of its different posologies when demonstrating non-inferiority when compared against Moxifloxacin and Gatifloxacin in the treatment of conjunctivitis	

Sponsor's name: Laboratorios Sophia, S.A. of C.V.

Finished Product Name: NA

Active Ingredient Name: Pazufloxacin

Methodology

Multicentric double randomized study masked.

Number of participants: 300 eyes, 60 eyes per treatment group

Diagnosis and main criteria for inclusion

Patients with bacterial conjunctivitis (signs and / or symptoms and / or culture)

Subjects aged 0 years to 99 years.

Study medication:

Pazufloxacin

- **Treatment duration:**
- - **Recruitment period: 4 months**
- - **Period of treatment: 7 days**
- - **Period of follow-up: 15 days**

Criteria for evaluation:

Efficacy measurements:

Main efficacy criterion

It will be determined as effective if there is a reduction in the number or species of bacterial flora comparing the basal culture against the final between the five different groups of patients and / or if there is a reduction or absence of the infection with the clinical evaluation through signs and symptoms such as: burning, tearing, foreign body sensation, pruritus,

photophobia, conjunctival hyperemia, chemosis, secretion, palpebral edema, membranes and / or pseudomembranes, palpebral scales and epitheliopathy

Security measurements:

Visual ability

Adverse events

INDICE

1. Summary of the study	2
2. Glossary and definitions	6
3. Administrative structure of the study	7
3.1 Parties not sponsored.	7
3.2 Sponsored parties	8
4. Background information	8
4.1 Justification	9
4.2 Non-clinical pharmacology	11
5. Clinical Studies	17
6. Hypothesis and Objectives	17
6.1 Work hypothesis	17
6.2 Objectives.	19
7. Point or points limit	19
8. Study plan	25
9. Measures to minimize deviations	29
10. Products administered	30
11. Description of the packaging	31
12. Management of the study medication	31
13. Closure of the center	33
13.1 Premature discontinuation of study	31
13.2 Center closure	31
14. Source data	33
15. Selection and withdrawal of subject of study	33
15.1 Inclusion criteria	33
15.2 Exclusion criteria	34
15.3 Criteria for patient withdrawal	36
16. Treatment of the study subjects	37
16.1 Managed treatments	37
16.2 Delivery of treatment	37
16.3 Previous and concomitant treatments	37
16.4 Treatments authorized during the study	39
16.5 Drug compliance	39
17. Methods and times of measurements	39

2. GLOSSARY AND DEFINITIONS

EA	Adverse Event
AV	Visual acuity
CV	Visual Capacity
FRC	Case Report Form
BPC	Good Clinical Practices
ICH	International Harmonization Conference
CI	Informed Consent
MY	Researcher's Manual
CIE	Independent Ethics Committee
CCI	Informed Consent Letter
CRI	Institutional Review Committee
ITT	Population Evaluable for Intent to Treat
IOP	Intraocular Pressure
PP	Estimatable Population by Proper Protocol
EAS	Serious Adverse Event
AMI	File Master of the Investigator
AME	Master Studio File
CP	Rear Camera
ME	Study Medication

3 ADMINISTRATIVE STRUCTURE OF THE STUDY

3.1 Non-sponsoring parties

A central microbiological laboratory will be responsible for collecting and processing conjunctival sac fundus samples.

4 INFORMATION ABOUT BACKGROUND

4.1 INTRODUCTION

Conjunctivitis (partial or total inflammation of the conjunctiva) caused by an external pathogen can be divided into bacterial and viral, however we must not forget that if we take into account its etiology we can name by fungal, allergic, autoimmune and by physical means (heat burns, friction, chemical).

In the following document, we will concentrate on exposing the epidemiological and clinical panorama of conjunctivitis caused by pathogens (bacteria and viruses) and the suffering related to the mass.

Currently about 6 million cases are registered per year in the general consultation (1% of the total annual consultations), this does not mean that all cases will be sent to the ophthalmologist, however as a reason for consultation 70% of the subjects come first with a family doctor and 35% refer to ophthalmologists because it is a case that does not remit with symptomatic or because the severity warrants it.

The cost of treating conjunctivitis according to data collected in the American union represents more than 377 million dollars a year.

Viral conjunctivitis:

Viral conjunctivitis represents an average of 80% of reported cases, it is estimated that 50% of these will be misdiagnosed as bacterial, this when compared to positive cultures.

65-90% of cases are caused by adenoviruses found in any of its two pathogenic entities, either in the form of epidemic keratoconjunctivitis or pharyngo-conjunctival fever. Clinically both are characterized by local inflammatory reactions, hyaline secretion, chemosis, photophobia, hyperemia, corneal deposits and lymphadenopathy.

The adenovirus is highly contagious and an estimated 10 to 50% chance of spread. 46% of the cultures in the hands of patients diagnosed with keratoconjunctivitis are positive, so their spread is verified mainly by contact and fomites.

Its incubation period ranges from 5 to 12 days and its transmission period of 10-14 days.

Its treatment consists of treating the symptoms with eye lubricants, NSAIDs, eye antihistamines, cold compresses, etc. Prophylaxis with antibiotics is not indicated since its benefit has not been proven, more if complications and delay in diagnosis of other entities are reported.

Bacterial conjunctivitis:

Its incidence is estimated at 135 per 10,000 inhabitants. The main routes of infection are by contact, although the proliferation of normal flora can occur as sole etiology or concomitantly.

The pathogenesis usually involves the disruption of the ocular surface defense mechanisms, due to trauma, tear film dysfunction or palpebral abnormalities, etc.

Usually its installation occurs 1 to 2 days after contact, characterized by rapid appearance of clinical signs such as palpebral edema, hyperemia, mucopurulent secretion, membranes and / or pseudomembranes.

The main infectious agents in adults are *H. influenzae*, staphylococci and streptococci. *H. influenzae*, *S pneumoniae*, and *Moraxella catarrhalis* are the most frequent agents in children. The course of the clinical picture is 7 to 10 days long.

Due to its clinical presentation, it is convenient to divide them according to their installation time, in acute, acute or chronic hyperinflation, and can guide diagnostic tests and empirical treatment according to the time of presentation.

Common pathogens according to the time of evolution

Acute	Híper Acute	Chronic
Staphilococcus Aureus.	Neisseria Gonorreae.	Moraxella catarrhalis.
Streptococcus pneumoniae.	Neisseria meningitidis.	Moraxella Lacunata.
Haemophilus influenzae.		Enterobacterias.

Special conditions:

In sexually active subjects who do not give up the clinical picture with empirical treatment (ceftriaxone 1gr b.i.d), we should investigate *Chlamydia Trachomatis* and add the relevant treatment.

In the case of infants or minors (less than 2 years old), we should consider granting systemic treatment because 50% of them concur with infections in other systems.

In oculo-vaginal infections we must investigate on strains compatible with trachoma (A-C); since we must remember that it affects more than 40 million subjects in areas of poor hygiene and continues to be a leading cause in non-reversible blindness.

4.1 JUSTIFICATION

Conjunctivitis and bacterial keratitis are the pathologies of the ocular surface most commonly found in our environment. In general, they resolve spontaneously, however if they are not treated properly they can have irreversible consequences for visual health

(corneal ulcers, endophthalmitis, etc.), especially in patients who will be operated on ophthalmic surgery and / or senile, children, contact lens wearers, among others.

These pathologies do not respect age, gender or social status. They are transmitted through contact with flush when talking to an infected person or through touch - hand - eye. Hence, it is quite common. The acute form of the infection is usually caused by *Haemophilus* species, *S. pneumoniae*, *S. aureus* or *epidermidis*, some of them normal habitual residents of the human conjunctiva.

Its management, sometimes represents a diagnostic and therapeutic challenge for both the general practitioner and the ophthalmologist. The etiology of it is a very useful guidance to improve the patient's prognosis. Much of the morbidity produced by this pathology can be lessened with adequate therapy by reducing treatment time and comfort. Hence the importance of knowing the ocular pathogens commonly associated with our environment, isolating them in an accurate manner and correlating them with the specific characteristics of the patient.

There are innumerable reports in the literature in this regard, however we have no knowledge of a specific one in our geographical area. The prevalence of *Staphylococcus aureus* 80 (23.7%), *Staphylococcus albus* 65 (19.2%), *Pseudomonas aeruginosa* 34 (10.1%), *Streptococcus pneumoniae* 29 (8.6%), *Haemophilus influenzae* 26 (7.7%), *Streptococcus pyogenes* 20 has been recently published. (6.2%), *Klebsiella pneumoniae* 18 (6.2%) *Escherichia coli* 15 (4.4%), *Neisseria gonorrhoeae* 13 (3.9%), *Streptococcus viridans* 11 (3.5%), *Moraxella catarrhalis* 10 (3.0%), among others, found that The most frequent isolations were made from the conjunctiva (66.7%) in contrast to the cornea (20.1%). These data correspond to the majority of what is published, however the socioeconomic and environmental conditions of the place where they were carried out are not the same to our region.

In other regions, such as India (with characteristics probably similar to our environment) it is observed that *S. Aureus* frequently causes infections of the eyelids and conjunctiva, *S. pneumoniae* is responsible for those inherent to the lacrimal apparatus and *S. coagulase negative* corresponds to infections intraocular.

In 10-year reviews in developed countries (eastern US) 1997- 2008, a tendency is observed in turn to the prevalence of *Staphylococcus Aureus* as the main ocular pathogen.

The effectiveness of 4th generation quinolones in the treatment of bacterial conjunctivitis since 1 year of age with a posology that varies from 2 to 4 times a day has been demonstrated in recent evidence, which corresponds to the preclinical studies and phase I of the drug. viii

We can also state the following points that support its use in infants and children under 18 years.

Due to the satisfactory results of the phase I study of the medication carried out in the adult population, in a phase II its implementation is justified in the child population since the evidence collected in said study allows inferring that its use is safe and effective to use it in the model of proposed disease, bacterial conjunctivitis. ix

Also the incidence of adverse events of musculoskeletal toxicity in children with chronic use of quinolones of 4th generation is reported as not significant at 5-year follow-up, so it was concluded that its use is adequate in this population. viii, ix

Currently, up to 26% resistance to the 4th generation quinolones (moxifloxacin, gatifloxacin and levofloxacin) is reported in strains of methicillin-resistant *Staphylococcus epidermidis*, so pazufloxacin represents a treatment option in such cases. ix, x

Sophia S.A de C.V. has developed a new ocular topical formulation belonging to the group of the fourth-generation quinolones, called Pazufloxacin mesylate, which has shown through in vivo and in vitro studies to have greater antimicrobial activity against methicillin-resistant *S. aureus*, *Haemophilus influenzae* ampicillin resistant, as well as *E. coli*, *Proteus mirabilis*, *Serratia marcescens* and *P. aeruginosa*. It should be noted that this formulation is free of preservatives.

Initially indicated for all those patients with bacterial conjunctivitis to susceptible organisms.

Pazufloxacin has been clinically shown to be equally effective in the prophylaxis and control of ocular infections when compared to gatifloxacin, moxifloxacin, and levofloxacin in models of *Staphylococcus aureus* infections. This is the reason why we are interested in determining the consistency of these results with the Pro-157 formulation developed by Laboratorios Sophia SA de CV.

4.2 NON-CLINICAL PHARMACOLOGY

Distribution of pazufloxacin in vivo iv

Sophia Laboratories were tested with three independent experiments in rabbits, which were separated into 6 groups, and slaughtered at times 15, 30, 60, 90, 120, 180 minutes to which they were applied exactly and only once 30 μ L of the formulation under study (pazufloxacin 0.3%). The cornea and the aqueous humor were extracted and stored at -20 ° C until the determination of pazufloxacin by HPLC.

Distribution of pazufloxacin in cornea

Table 1 shows the average concentration of pazufloxacin found per mg of cornea.

Table 1. Average concentration of pazufloxacin found per mg of cornea

Minutes	ng Pazufloxacin / mg cornea
15	3.9
30	3.2
60	2.4
90	2.0
120	1.4

Calculation of pharmacokinetic parameters

[figure not shown]
An entry is assumed as if it were intravenously and a first-order model of corneal removal. It also considers a volume of distribution in cornea of 0.08mL. It is considered that 30 mL of a solution of 3mg / 1000 μ L was added, which corresponds to a total amount of 90,000 ng of pazufloxacin, Table 1.

With regard to the concentrations in multiple dosing regimen, it can theoretically be said that the max and min concentrations of the drug follow different administration intervals (Table 3), based on pharmacokinetic parameters obtained from a single administration (Table 2, graphs 1 and 2).)

Table 2. Pharmacokinetic parameters for pazufloxacin in cornea, calculated from the results of table 1.

Parameter	Value
(kep) Constante de permeabilidad de la barrera epitelial	0.00083 cm \cdot hr $^{-1}$
(k) Constante de eliminación	0.0094648 min $^{-1}$ 0.567889 hr $^{-1}$
(t _{1/2}) Vida media	73.2 minutos
(F) Fracción absorbida	0.00388 0.388%.
AUC Área bajo la curva	459.4 ng/mg min

Graph 1. Representation of the behavior of the kinetics of pazufloxacin in the cornea following a first order reaction, simulating different dosage intervals.

Graph 2. Simulation of levels of pazufloxacin in cornea in vivo, dosing on the first day from 8 a.m. at 10 p.m. and resuming treatment at 6 a.m. of the next day.

[figure not shown]

Table 3. Maximum and minimum concentration in cornea in vivo (theoretical) reached in equilibrium, considering different dosage intervals.

Hora	Cmax (ug Pazu/mg córnea)	Cmin (ug Pazu/mg córnea)
1	10.070	5.707
2	6.428	2.064
3	5.334	0.971
4	4.865	0.502
5	4.634	0.271
6	4.513	0.150
7	4.447	0.083
8	4.410	0.047
9	4.390	0.026
10	4.378	0.015
11	4.372	0.008
12	4.368	0.005

Distribution of pazufloxacin in aqueous humor

For the calculation of pharmacokinetic parameters, a compartment model with first order absorption and elimination was followed. The volume of distribution for the aqueous humor of 0.25 mL, administration of 30 μ L of a solution of 3mg / 1000 μ L is considered, a total amount of 90,000 ng is obtained, Table 4 shows the average concentration found of pazufloxacin per mL of aqueous humor (Table 5).

Table 4. Average found concentration of pazufloxacin per mL of aqueous humor.

Minutos	ng Pazufloxacino/mL Humor acuoso
15	211
30	295
60	499
90	590
120	472
180	365

Table 5.- Pharmacokinetic parameters for pazufloxacin in aqueous humor, calculated from table 4.

[figure not shown]
Parámetro	Valor
(k) Constante de eliminación	0.005129 min ⁻¹ 0.3078 hr ⁻¹ .
(ka) Constante de absorción	0.02835 min ⁻¹ 1.70008 hr ⁻¹
(t _{max})	73.6 min
(t _{1/2}) Vida media	135 min
(F) Fracción absorbida	0.002 0.2%
AUC Area bajo la curva	136275 ng/mL min

The max and min concentration of the drug can theoretically be predicted by following different administration intervals (Table 6), based on pharmacokinetic parameters obtained from a single administration (table 5, graph 3 and 4).

[figure not shown]
Table 6 Maximum and minimum concentration in aqueous humor reached at equilibrium considering different dosage intervals

horas	t max eq(hrs)	Cmax ng/mL	Cmin ng/mL
1	0.42	2389	2246
2	0.69	1265	1033
3	0.87	914	579
4	0.98	752	362
5	1.05	663	240
6	1.10	609	165
7	1.14	574	115
8	1.16	550	82
9	1.18	534	59
10	1.19	523	42
11	1.20	515	31
12	1.21	509	22

Graph 3. State of equilibrium in aqueous humor in different dosing times

Graph 4.- Continuous administration during the day of 8 a.m. at 10 p.m. resuming treatment at 6 a.m. of the next day.

We also performed a preclinical study (PRO-0157-PZ), comparative randomized, unicentric, prospective, longitudinal and blinded in 30 rabbits (60 eyes) albino males New Zealand, whose objective was to compare and evaluate, safety as the toxicity of the topical ophthalmic solution of pazufloxacin vs Moxifloxacin hydrochloride and Gatifloxacin in the ocular surface in a clinical and histological manner.

The allocation to the treatment group was randomly 1: 1, 10 rabbits were assigned for each treatment group, for purposes of the analysis both eyes were evaluated so the total number of eyes analyzed per treatment group was 20. The variables evaluated were:

Conjunctival hyperemia, corneal surface, fluorescein staining, lysamine green stain and tonometry, presence of adverse events, red eye, lacrimation, findings in the revision of the periocular area and the anterior segment, findings in fundoscopy. In the histopathological study, histological changes were evaluated, as well as the toxicity in cornea, conjunctiva, ciliary body and retina.

The results obtained showed that in the different visits very few cases were found with the presence of sign in the rabbits, also, when making the intergroup comparisons, only statistically significant differences were found ($p = 0.036$) for the variable chemosis in the evaluation corresponding to the day 30, where there were 4 (20%) reported cases in an area smaller than 25% of the total, 4 (20%) cases between 1 and 3, in the Moxifloxacin group a total of 11 (55%) cases were reported in an area smaller than 25% of the total, 4 (20%) cases between 1 and 3, while in the Gatifloxacin group there were 4 (20%) and 2 (10%) cases respectively.

It should be noted that in the rest of the variables evaluated the differences found were not statistically significant ($p <0.05$)

5 CLINICAL STUDIES

A phase I clinical study was conducted to evaluate the safety and tolerability of the PRO157 ophthalmic solution in healthy volunteers. The tolerability was determined by the presence of: burning, hyperemia, chemosis, foreign body sensation and lacrimation. Safety by assessing visual acuity and / or visual capacity, fluorescein staining, green lysine and intraocular pressure and the frequency of adverse events. A total of 5 visits were made.

- Visit 0: Basal, day 0 (selection period).
- Visit 1: Follow-up, day 2 (treatment period).
- Visit 2: Follow-up, day 4 (treatment period).
- Visit 3: Follow-up, day 7 (treatment period).
- Visit 4: Final day 11 (final visit).

During which time the drop was applied 4 times a day in both eyes, the results that were obtained determined that the variables that reflect tolerability of the product, such as ocular burning, red eye, conjunctival hyperemia and lacrimation, remained predominantly in a low intensity (mild). There was no presence of chemosis or secretion. More than 88% of the eyes studied showed no sensation of a foreign body in the eye and more than 70% of the eyes did not present pruritus in the different evaluations. Variables that reflect the safety of the product, such as visual capacity and intraocular pressure, were always within normal parameters. No findings were reported during the revision of the anterior segment or the posterior segment, none of the eyes studied showed any degree of fluorescein or green lysine uptake in the corneal surface, there were no reports of adverse events. Vi

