• The safety of the use of PRO-157 will be evaluated in the visits indicated in the schedule, through the following parameters:

1. Visual capacity
2. Eye surface
3. Exploration of the previous segment
4. Exploration of the posterior segment
5. Burning
6. Foreign body sensation
7. Lachrymation
8. Conjunctival hyperemia
9. Itching
10. Photophobia
11. Chemosis
12. Tear discharge
13. Eyelid edema
14. Membranes / pseudomembranes
15. Scales
16. Corneal epithelial defects
17. Adverse events

It will be considered that the drug under evaluation is safe for use in humans if there are no changes in the parameters indicated in more than 5% of the subjects, in both eyes, if the

patient goes to all the visits of the study and complies with adherence to treatment $\geq 80\%$ during the time of evaluation of the study.

Variable	Operationalization	Measurement scale	Value
Visual ability	Independent Discrete quantitative	Points logMAR 0-1 0 = Snellen 20/20	Do not present change in 1 line in the Snellen letter or in 1 logarithmic point (log MAR)
Ocular surface	Dependent Qualitative ordinal	Absent Present	Abnormalities in any area of the ocular Surface
Exploration of the previous segment	Dependent Qualitative ordinal	Normal Abnormal	Abnormalities in any of the structures included: cornea, iris, pupil, irido-corneal and crystalline angle.
Exploration of the posterior segment	Dependent Qualitative ordinal	Normal Abnormal	Abnormalities in any of the structures included: vitreous, retina, macula and the optic nerve
burning	Dependent Qualitative ordinal	Absent Present	Must be recorded as absent in 95% of the subjects evaluated
strange body sensation	Dependent Qualitative ordinal	Absent Present	Must be recorded as absent in 95% of the subjects evaluated
tearing	Dependent Qualitative ordinal	Absent Present	Must be recorded as absent in 95% of the subjects evaluated

Secretion	Dependent Qualitative ordinal	Absent Present	Must be recorded as absent in 95% of the subjects evaluated
Conjunctival hyperemia	Dependent Qualitative ordinal	Absent Mild Moderate Severe	You must comply with the following: Absent ≥ 95.0% Mild ≤ 5.0% Moderate ≤ 2.5% Severe ≤ 1.0%
Photophobia	Dependent Qualitative ordinal	Absent Mild Moderate Severe	You must comply with the following: Absent ≥ 95.0% Mild ≤ 5.0% Moderate ≤ 2.5% Severe ≤ 1.0%
Chemosis	Dependent Qualitative ordinal	Absent Present	Must be recorded as absent in 95% of the subjects evaluated

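### The fixed safety limits for burning, foreign-body sensation, tearing and hyperemia, and the 5% change rule over them, are unjustified, fit poorly with the sponsor's own Phase I summary and cannot separate drug irritation from disease.

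*Combined protocol and SAP*

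**What the plan says.** Section 7.1 (security measurements) lists 17 safety parameters. PRO-157 counts as safe if these do not change in more than 5% of subjects, in both eyes, given full attendance and at least 80% adherence. A table then sets a value for most parameters. For burning, foreign-body sensation and tearing the entry is "Must be recorded as absent in 95% of the subjects evaluated". Hyperemia must be absent in at least 95% and mild in at most 5%, with tighter caps on moderate and severe. Itching is ninth in the list but has no row in the table.

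Section 5 summarises a Phase I study run to "evaluate the safety and tolerability of the PRO157 ophthalmic solution in healthy volunteers", in which "the drop was applied 4 times a day in both eyes". It reports:

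- Foreign-body sensation: "More than 88% of the eyes studied showed no sensation of a foreign body in the eye and more than 70% of the eyes" (the second figure begins the statement on pruritus).
- Pruritus: "more than 70% of the eyes did not present pruritus in the different evaluations".
- The rest: "ocular burning, red eye, conjunctival hyperemia and lacrimation, remained predominantly in a low intensity (mild"), with no percentage free of any of them.

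It reports no adverse events.

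Section 8 plans 60 eyes per group, gives PRO-157 two, three or four times a day, and adds an artificial tear four times a day in every arm. Sections 6.1 and 6.2 state both the safety hypothesis and the safety objective against moxifloxacin and gatifloxacin.

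**The concern.** A safety threshold should be one that an acceptable product usually meets and an irritating one usually misses. Three things suggest that these limits do not work that way.

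- The only Phase I percentage for a symptom with a 95% limit is a lower bound of 88%, in uninfected eyes. Nothing in the protocol explains why 95% was chosen or sets it beside that result.
- Trial patients are enrolled because they have conjunctivitis. A symptom present at day 3 or day 8 may be infection that has not yet cleared (Section 4.1 gives a course of 7 to 10 days) or irritation from the drop. A limit on absence within one arm cannot tell which.
- The governing sentence counts changes without giving a direction. A patient whose burning resolves has changed, so a successful treatment could breach the rule.

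The risk is that PRO-157 is called unsafe for mild effects already seen in Phase I, or that the rule is set aside once the data are known.

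**Working it through.** **The plan's own figures.** No operating characteristic is given for the safety limits. The only computed design figures are the sample sizes in Section 23 (147 and 44 per group). The Fleiss formula with continuity correction returns 148 and 44, so they reproduce to within rounding, but they do not bear on this rule.

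**Inputs for the check.**

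- Limit: absent in 95% (Section 7.1).
- Arm size: 60 eyes (Section 8). The limit is worded in subjects, so 30 subjects with two eyes each is shown as an alternative. That is an assumption.
- True rate without foreign-body sensation: more than 88% in Phase I (Section 5). This is a lower bound, so a range is used.

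**Formula.** Let X be the number with the symptom, binomial with n units and probability p = 1 − absence rate. With n = 60 the limit needs at least 0.95 × 60 = 57 free of it, so X ≤ 3. With n = 30 it needs at least 28.5, hence 29, so X ≤ 1.

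**Worked case, absence rate 88% (p = 0.12), n = 60.**

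- P(0) = 0.88^60 = 0.0005
- P(1) = 60 × 0.12 × 0.88^59 = 0.0038
- P(2) = 1770 × 0.12² × 0.88^58 = 0.0153
- P(3) = 34220 × 0.12³ × 0.88^57 = 0.0405
- Sum = 0.060

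With n = 30: 0.88^30 + 30 × 0.12 × 0.88^29 = 0.0216 + 0.0884 = 0.110.

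**Chance of meeting the one foreign-body limit in one arm:**

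| True absence rate | 60 units | 30 subjects |
|---|---|---|
| 88% | 6% | 11% |
| 90% | 14% | 18% |
| 92% | 28% | 30% |
| 95% | 65% | 55% |
| 98% | 97% | 88% |

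A product sitting exactly on the limit therefore misses it about one time in three with 60 units (1 − 0.65 = 0.35).

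**What cannot be computed.** Burning, tearing and hyperemia have no Phase I percentage, so no pass probability can be attached to them. The two- and three-times-daily regimens have no Phase I data.

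**Fit with the objective.** Sections 6.1 and 6.2 ask whether PRO-157 is as safe as each comparator. The limits in Section 7.1 refer to no comparator. Two arms with the same day-8 symptom rate, one from slow clearance and one from irritation, would be treated alike.

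**The case against.** A reader might infer that Phase I has already missed the limits for all four symptoms, and that the rule must fail whatever the trial shows. The documents do not support this.

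- Only foreign-body sensation has a figure, and it is a bound. Under this model, and if Phase II rates match Phase I, 6% is the lowest pass probability consistent with it for 60 units.
- The statement that the other signs "remained predominantly in a low intensity (mild") may describe intensity among affected eyes only.
- The 70% figure is for pruritus. Itching has no 95% row, and Section 5 reports its presence, not change from baseline, so no pass probability against the 5% change rule follows from it.
- Two of the three PRO-157 arms use lower frequencies than Phase I. All patients also get an artificial tear, and Section 5 mentions none.
- Phase I counts eyes and the limits count subjects. The change rule adds a both-eyes condition that may make it looser. Two eyes of one patient are also correlated, so 60 independent units is a simplification.
- The visit at which the limits are read is not stated.

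All of this stands, and it rules out any claim of certain failure. It does not justify the limits or tie them to a comparator, and it does not answer the mixing of disease with irritation, which holds at any frequency. It is also fair that the safety objective itself rests on adverse events and visual capacity, but that does not cancel the rule in Section 7.1.

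**Conclusion.** The concern holds in limited form. The fixed limits are unjustified and hard to reconcile with the Phase I summary at four times a day. For foreign-body sensation the chance of meeting the limit runs from 6% to 97% (60 units), or 11% to 88% (30 subjects), as the true absence rate goes from 88% to 98%. This assumes independent units and one symptom in one arm. For burning, tearing and hyperemia the tension is plausible but cannot be sized.

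The firmer part needs no arithmetic. In patients who enter with these symptoms, a limit on absence mixes residual infection with drug effect, and the change criterion counts improvement. For these symptoms the rule therefore does not measure safety, and it does not match the comparative hypothesis and objective.

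**What to change.** For burning, foreign-body sensation, tearing, itching and hyperemia, replace both parts of the rule in Section 7.1: the fixed absence limits (itching has none to remove) and the 5% change criterion. Changing the table alone would leave the governing sentence in force.

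In their place, report by arm the proportion of patients with a symptom that is new or worse than at baseline, at day 3 and at day 8. Give each PRO-157 arm's difference from moxifloxacin and from gatifloxacin with a 95% confidence interval. State that the patient is the unit. Show the Phase I rates by visit alongside.

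The cost is an edit to the safety table and its governing sentence and one paragraph in Section 23. The schedule already records these symptoms at baseline, day 3 and day 8, so no new data are needed. The downside is that the absolute pass mark for these symptoms is lost.
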